4. **Research Plan:** Summarize the study design and research procedures using non-technical language that can be readily understood by someone outside the discipline. **Be sure to distinguish between standard of care vs.** research procedures when applicable, and include any flowcharts of visits specifying their individual times and lengths. Describe the setting in which the research will take place.

Overview of Study Design

This single-site, proof-of-concept, clinical trial is a double-blind, placebo-controlled, parallel group study to test the effectiveness of naltrexone + bupropion (NB) pharmacotherapy in BED patients with and without obesity. BED patients with (BMI > 30 and <50) and without obesity (BMI >21.5 and <29.9), will be randomized to NB (32 mg/day naltrexone combined with 360 mg/day bupropion) or placebo (n=50 per cell, n=200 total).

Following eligibility screening and randomization, participants will start a 12-week medication treatment period, a treatment period consistent with other BED medication trials (McElroy et al., 2016). Participants will have four weeks of up-titration: one tablet daily (Naltrexone 8mg/ Bupropion 90mg; 1 week), then two tablets daily (Naltrexone 16mg/ Bupropion 180mg; 1 week), then three tablets daily (Naltrexone 24mg/ Bupropion 270mg; 1 week), to reach the full dose of four tablets daily (Naltrexone 32mg/ Bupropion 360mg). The dosage will continue for the remainder of the 3 months. Medication will be discontinued at the end of 3 months, and patients will then be followed 12-months post-treatment to assess the durability of medication effects. The primary outcome measure is reduction in binge-eating frequency.

To evaluate correlates and mechanisms of NB on eating behavior, assessments will occur in the laboratory and in the field to optimize internal and external validity. Participants will complete human laboratory sessions ("lab sessions") before the start of medication and then during the final week of the 12-week medication period to evaluate the ability to resist eating preferred high-caloric food and subsequent overeating. During the laboratory sessions, we will evaluate potential mechanisms including eating peptides

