### Procedures for Modeling Cue-Induced Eating Behavior.

Each participant will complete two laboratory sessions, the first scheduled prior to starting medication, and the second at the end of medication treatment (week 11-14). This pre-post evaluation by medication group will provide a powerful test of medication effects. Alternatively, if the pre-treatment laboratory session cannot be schedule prior to the beginning of treatment, participants may complete the session around one month of treatment (week 4-6). If we are unable to reschedule at the HRU/CSRU, the lab session will take place at [name] in dedicated lab rooms in [name] research space. Our previous eating study (HIC# 0909005678, [name]) took place in this setting and was very successful. There will be no blood collected throughout the lab session if it occurs at [name], but baseline samples will be obtained on the 4th Floor YCCI unit. All other lab procedures will remain the same. Participants will not be excluded from the treatment study if they are not willing to do the lab sessions, or if they are not able to be scheduled for the lab sessions. Research procedures related to the treatment study (e.g., blood draws for liver function, lipids, and metabolic function) will still be drawn if lab sessions are not completed.

Laboratory sessions will be completed at the Hospital Research Unit (HRU) of the Yale Center for Clinical Investigation (YCCI) located at Yale-New Haven Hospital or the Church Street Research Unit (CSRU) at [name]. Participants will be instructed not to eat past 10:00pm the night before the laboratory session. They will arrive at the HRU/CSRU at 7:30am. At the start of the lab session, participants will have an IV cannula inserted and complete the baseline assessments listed in **Table 1**. Participants will then receive breakfast to standardize time since last food consumption. Breakfast will be a breakfast bar that is approximately 150 calories provided by the Research Team. Participants will then be food deprived for the next 3 hours. Based on our prior work, this length of food deprivation is sufficient to increase food craving. After 3 hours of food deprivation, participants are presented with preferred high-caloric snacks. Participants will be asked to take their study medication prior to the second lab session. Scheduling is limited to HRU/CSRU and participant availability.

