regarding eating behavior with self-initiated, scheduled, and random prompts to a smartphone. We will provide participants with the wearable biosensor (Garmin Vivosmart 4) and an Android cell phone to use that has the app installed where they will respond to daily prompts. If the equipment is not available when a participant is to start the treatment phase, they will not complete the Biosensor component.

Monitoring Stress Levels. To monitor ambulatory stress levels, we will use Garmin bands. These bands provide a 'stress score' (range 1-100) with a 3-minute granularity. The algorithm is proprietary, but Garmin acknowledges that one of the primary factors in the algorithm is heart rate variability (HRV). HRV is the beat-to-beat variation in heart rate, which has been shown to be associated with emotion regulation and likely contribute to binge eating . We have shown that stress and substance use produce dynamic changes in HRV , and that HRV may be used as a stress indicator. With values provided every 3 minutes, we can model how dynamic changes in HRV are predictive of binge eating. We also plan to evaluate how location (e.g., GPS) affects stress levels and subsequent eating behavior. The Garmin band also provides daily metrics on steps, distance, heart rate, sleep duration, and sleep level classification. Access to this data is through a Garmin service to academic researchers https://developer.garmin.com/health-api/overview/. Data obtained from bands will be continuously transmitted to the mHealth Core Facility at UMass.

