### 13. **Statistical Considerations:** Describe the statistical analyses that support the study design.

Baseline demographic and clinical characteristics for the randomized groups will be compared using chi-square tests for categorical variables, and ANOVA or Kruskal-Wallis tests for continuous variables. Continuous variables will be examined for normality using normal probability plots and Kolmogorov-Smirnov test statistics. If normality is not satisfied, transformations or nonparametric alternatives will be considered. Dropouts and completers will also be compared. Primary analyses will be based on an intent-to-treat basis. Primary outcomes will be tested at the two-sided alpha 0.05 threshold. Secondary analyses will be adjusted for multiple tests using the Bonferroni correction basing the adjustment on the number of conceptually related statistical tests within each hypothesis.

Overall analysis strategy. Mixed-effects models [92] will be used to compare treatments. These models allow for different numbers of observations per subject, use all available data on each subject, and are unaffected by randomly missing data. A further advantage is the capacity to test and account for individual-difference contributions to the treatment outcomes (Cudeck, 1996; Cudeck & Klebe, 2002; Hedeker et al., 1996; Hedeker & Gibbons, 1996; Singer, 1998). They provide flexibility in modeling the correlation structure of the data. In models for each outcome in Aims 1 & 2, we will include obesity status (obese vs. non-obese) and treatment (NB vs. placebo) as between-subject effects, time (see Aim-specific study time points) as a within-subjects factor, and subject as the clustering factor. Across analysis, time-points associated with the 12-week treatment phase will be considered as primary outcomes, and all analyses will be repeated to examine change

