during the 12-month follow-up period. All possible interactions will be modeled and the following primary a priori contrast will be tested: 1) placebo NB vs. active NB. Least-square means will be plotted and compared post-hoc to interpret significant effects. Because we cannot a priori predict the shape of the response over time in each arm of the trial we will first treat time as a categorical predictor and will then test for polynomial trends over time. We will consider different error structures (e.g., AR1, CS, independence) and select the best fitting one based on Schwartz' Bayesian Criterion (BIC). We will compare dropout patterns between groups and if there are concerns of informative dropout or informative intermittent missing data, we will use pattern mixture models [93] to perform sensitivity analyses. Secondary models will include subjects with complete data. To test for assessment reactivity, we will evaluate whether biosensor assessment (yes/no; between-subject variable) moderates our primary outcomes in Aim 1 (as either a main effect, or interacting with medication). If this is found, then all subsequent analyses for Aims 1 & 2 will be limited to the sample (n=140) without the biosensor assessment.

Primary Aim 1. We will use the mixed models described above to test the effectiveness of NB medication for BED patients with and without obesity. The primary aims are to evaluate NB medication for (a) reducing binge eating frequency; and (b) in the patients with obesity, for reducing % weight loss. Significant NB main effects (regardless of obesity status) on frequency of binge eating will be considered supportive of our primary hypothesis. We also expect that NB will be associated with significantly greater reductions in % weight loss among the BED+obese group. In view of the factorial design, we will also be able to assess whether obesity status moderates reductions in binge eating frequency. These analyses will focus on 12-week outcomes. Secondary analysis will be repeated to examine change during the 12-month FU period.

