  - e) Distributes the investigational device to subjects enrolled in the IRB-approved protocol: Subjects will not receive the Biosensor until they have reviewed/agreed/signed a Consent Form, completed the intake process to determine eligibility, and completed the first lab session. Only a subset (n=60) will participate.

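### The assessment-reactivity check rests on a biosensor contrast that was not randomised, so a main effect may reflect who completed lab session 1 and could needlessly drop 60 of 200 participants

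*Combined protocol and SAP*

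**What the plan says.** **The test and its consequence** (Section I, 13, Overall analysis strategy). The plan says: "To test for assessment reactivity, we will evaluate whether biosensor assessment (yes/no; between-subject variable) moderates our primary outcomes in Aim 1". Either of two findings counts: "as either a main effect, or interacting with medication". If one is found, "all subsequent analyses for Aims 1 & 2 will be limited to the sample (n=140) without the biosensor assessment". No alpha is given for this check. The only stated threshold is "Primary outcomes will be tested at the two-sided alpha 0.05 threshold".

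**The numbers.** The Overview of Study Design plans "n=50 per cell, n=200 total", with 15 biosensor users per cell, 60 in all.

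**Who gets the device.**
- The Randomization paragraph (Section I, 4) allocates participants to NB or placebo. It says nothing about the device.
- Section II, Devices, item 4(e) lists what must come first, ending with "completed the first lab session. Only a subset (n=60) will participate".
- The biosensor procedures in Section I, 4 add an equipment condition: "If the equipment is not available when a participant is to start the treatment phase, they will not complete the Biosensor component".
- The laboratory procedures make the sessions optional: "Participants will not be excluded from the treatment study if they are not willing to do the lab sessions". A participant who cannot be scheduled also stays in the trial, and a first session that cannot be held before treatment may move to weeks 4-6.

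**The model.** Section 13 names obesity status, treatment and time as effects, with all interactions. It names no term for lab-session completion or enrolment period, and no comparison of users with non-users at baseline.

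**The concern.** The question the check is meant to answer is whether wearing the device and answering prompts changes binge eating. The comparison it makes is between two groups formed by other things as well. A user was willing and able to complete a pre-treatment session running from 7:30am to 3:30pm, went through that food challenge, and started treatment when a device was free. The non-users include everyone who declined or missed the session, and probably those whose first session slipped into weeks 4-6, inside the six-week monitoring window.

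If people who complete the session differ in outcome from those who do not, the main effect will show it even when monitoring does nothing. The plan would read that as reactivity and set aside 60 of 200 participants (30%). Aim 2 is more exposed than Aim 1, because every user has a first laboratory session and some non-users have none.

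**Working it through.** **1. The plan's own figure.** 4 cells x 15 = 60 users; 200 - 60 = 140 non-users. This reproduces the stated n=140.

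**2. False rejection of the main effect when monitoring has no effect.** Let d be the user/non-user difference in SD units due to selection alone. The documents give no value, so d is assumed. Two-sided alpha is taken as 0.05.
- SE = sqrt(1/60 + 1/140) = 0.154.
- Rejection probability = Phi(d/SE - 1.96) + Phi(-d/SE - 1.96).

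| d (assumed) | d/SE | Rejection, 60 v 140 | Rejection, 42 v 98 (30% attrition) |
|---|---|---|---|
| 0 | 0 | 5% | 5% |
| 0.1 | 0.65 | 10% | 8% |
| 0.2 | 1.30 | 25% | 19% |

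The last column uses SE = sqrt(1/42 + 1/98) = 0.184. The 30% is an assumption within the 20-38% attrition that the protocol cites for earlier pharmacotherapy trials in binge-eating disorder.

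**3. How large d might be.** Suppose completers and non-completers of the first session differ by D SD, and device availability among completers is arbitrary. All users are completers, while non-users are a mixture, so d = D x (non-completers / 140). With D = 0.4 (assumed):

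| Completion (assumed) | Non-completers | d | Rejection |
|---|---|---|---|
| 90% | 20 | 0.4 x 20/140 = 0.06 | 6.6% |
| 80% | 40 | 0.4 x 40/140 = 0.11 | 11.5% |
| 60% | 80 | 0.4 x 80/140 = 0.23 | 32% |

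**4. Simulation of the two trigger routes.** 4000 trials were simulated per setting. A latent engagement trait drove session completion, 15 users per cell were drawn from completers, and the linear model held treatment, obesity, their interaction, biosensor, and biosensor by treatment. Monitoring had no effect.
- In a middle case (60% completion, log-odds of completion 1 per SD of trait, trait-outcome correlation 0.3), the main effect rejected 15% of the time.
- With a trait unrelated to outcome and to the NB effect, it stayed near 5%.
- The medication interaction stayed near 5% unless the trait also modified the NB effect, when it reached 6-14%.
- With devices assigned at random within cells, the main effect rejected 4.9-5.1%. The inflation therefore comes from the missing random assignment.

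**5. Cost of a false trigger.** An effect with 80% power at 100 per arm is 2.80 x sqrt(2/100) = 0.396 SD. At 70 per arm the SE is sqrt(2/70) = 0.169, and power is Phi(0.396/0.169 - 1.96) = 65%. Similarly, 90% falls to 77%.

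For Aim 2, if 60-80% of participants have a first session (120-160 people, assumed), removing the 60 users takes 60/160 = 38% to 60/120 = 50% of them.

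**The case against.** The strongest reply is that the size is guesswork and probably small. The plan expects laboratory sessions from everyone: Aim 2 is set at all 200, and the laboratory procedures describe two sessions per participant, with missed sessions as exceptions. Many of the 140 non-users would then also be completers, which dilutes the contrast. **This stands.** At 80% completion, even a 0.4 SD completer gap gives only about 11.5%. Equipment availability may also be close to arbitrary, or tied only to calendar time.

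A second reply is that the model has repeated measures, so a stable severity difference need not appear as a difference in change. **This stands in part.** The plan does not say whether baseline is one of the time points. If it is, a biosensor main effect averaged over time includes the baseline difference, which monitoring cannot have caused. The plan's trigger is the main effect, not biosensor by time.

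A third reply is that 15 users per cell balances users and non-users on medication and obesity. **True**, but it does not balance engagement within cells. It is a quota with no stated method of filling it.

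A reader might go further, in three ways that the documents do not support:
- *That participants chose the device themselves.* The protocol is silent on how devices are allocated among those eligible. It does not describe self-selection.
- *That the restriction biases NB versus placebo.* If device use is fixed before dosing, treatment remains randomised among the 140.
- *That Aim 2 would lose its most complete participants, or that the difference would be published as reactivity.* Completing the first session does not show completeness at the second session or on outcomes, and no publication plan for this check is given.

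**Conclusion.** The point holds as a limit on what the check can show. As written, a biosensor main effect cannot separate reactivity from selection through the first laboratory session, yet by itself it is enough to remove 30% of the sample from later Aim 1 and 2 analyses.

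The loss is mainly power (80% to about 65% in the worked example) and generalisability. The absence of bias in NB versus placebo depends on device status being fixed before dosing.

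The rejection rates of about 10% and 25% rest on assumed differences of 0.1 and 0.2 SD and on an assumed 5% test. They are illustrations, not estimates, and shrink towards 5% as completion of the first session approaches 100%. The interaction route is much less exposed. This is a modest correction to a secondary check, not a threat to the main treatment comparison.

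**What to change.** In Section 13:
1. State that a biosensor main effect alone neither counts as reactivity nor triggers the n=140 restriction.
2. Run the comparison among participants who completed the first laboratory session before starting medication, users versus non-users, adjusted for baseline EDE binge frequency, obesity stratum and enrolment period. Define a user by device issue at treatment start, so that status is fixed before dosing and later entry to the Biosensor Arm does not change it.
3. Label the result an association, because the device was not randomly assigned.

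If enrolment is still open, allocate each remaining device by random draw within obesity stratum among consenting participants who have completed the first session. With a stated project end of September 2024 and 15 months of participation, this step may no longer be available. The wording changes would still apply.

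The cost is SAP text using data already collected, plus a short random list if devices remain to be issued. No visits are added. The downside is a smaller comparison group for the reactivity check, and without random allocation the adjusted comparison is still observational.

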### **SECTION I: RESEARCH PLAN**

1. **Statement of Purpose:** State the scientific aim(s) of the study, or the hypotheses to be tested.

**PRIMARY AIM 1.** To conduct a double-blind, placebo-controlled parallel group study to evaluate the efficacy of naltrexone HCI and bupropion HCI (NB) versus placebo in patients with binge-eating disorder (BED), stratified by obesity status (n=50 per cell, n=200 total).

- *Hypothesis 1.1.* We hypothesize that NB will be superior to placebo for reducing binge eating among patients with BED.
- Hypothesis 1.2. We hypothesize that NB will be superior to placebo for reducing weight among BED patients with obesity.
- Hypothesis 1.3. We will examine whether BED patients with and without obesity derive differential benefit of NB versus placebo on reducing binge eating (i.e., does obesity moderate outcomes).

**PRIMARY AIM 2.** To evaluate correlates and possible mechanisms underlying the effect of NB on binge eating among all participants (n=50 per cell, N=200 total). To evaluate the effect of NB on hypothalamic melanocortin and brain reward systems, eating behavior will be assessed with an established human laboratory paradigm designed to evaluate the ability to resist eating preferred high-caloric food and subsequent over-eating. We will evaluate potential mechanisms including eating peptides (leptin, ghrelin) involved in both homeostatic and hedonic aspects of eating, as well as food craving, mood, hunger, and control over eating.

Hypothesis 2.1. We hypothesize that potential medication-related changes in eating behavior, eating peptides and craving assessed in the laboratory will mediate clinical outcomes during the 12-week treatment period (i.e., rates of binge eating).

Hypothesis 2.2. We hypothesize that NB versus placebo will increase the ability to resist eating preferred high-calorie food, and will reduce overall calorie consumption in patients with BED.

Hypothesis 2.3. We will examine whether BED patients with and without obesity derive differential benefit of NB versus placebo with regards to their ability to resist eating or calories consumed (i.e., does obesity moderate outcomes).

**EXPLORATORY AIM 3**. To assess eating and drinking behavior, food craving, and mood 'in the field' in a subset of participants (n=60).

2. **Probable Duration of Project:** State the expected duration of the project, including all follow-up and data analysis activities.

September 2017 – September 2024

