(leptin, ghrelin) involved in both homeostatic and hedonic aspects of eating, as well as food craving, mood, hunger, and control over eating. Participants who are unable to complete a baseline lab session prior to the start of treatment may complete the lab session 4-6 weeks after beginning treatment. We believe that this period of time is sufficient to capture medication effects on eating behavior.

Finally, we plan to monitor ambulatory dynamic changes in stress with a wearable biosensor and collect daily information regarding eating behavior with self-initiated, scheduled, and random prompts to a smartphone 'in the field' during the first 6 weeks of the 12-week treatment period in a subset of participants (n=15 per cell, n=60 total; "Biosensor"). Eating and drinking behaviors will be tracked using an Android smartphone that is synced with a smartwatch (Garmin Vivosmart 4) to passively track stress states. During real-time episodes of calorie consumption, participants will be prompted to answer questions delivered to their smartphone related to food craving, mood, and stress.

[figure not shown]

Figure 1. Overview of Study Design

**Pre-Screening**: Participants responding to recruitment efforts will be screened by telephone. If participants prefer to answer some of the pre-screening questions through the Yale Qualtrics system, participants will indicate their consent to the recruitment/pre-screening process in the online system. After the initial telephone screening, potentially eligible participants will be scheduled for an in-person assessment; participants will complete survey measures of eating behaviors and psychopathology and psychosocial functioning around the time of the in-person appointment. Potential participants will meet with a research assistant who will obtain informed consent and will screen the participant for inclusion and exclusion criteria. Participants who provide informed consent and are determined to be eligible will then participate in the study as depicted and described in the following paragraphs. See also Figure 1.

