The system involves a smartwatch that participants will wear on their non-dominant hand. The system is linked to a smartphone. Participants will be provided with a phone to use for the study duration. Participants will wear the system for the first six weeks of the 12-week medication period (3 weeks medication titration + 3 weeks at full dosing). We believe that this period of time is sufficient to capture medication effects on eating behavior. These "real-time" consumption behavior data, along with associated proximal data regarding behavior, mood, and stress variables — will be analyzed within subjects over time (to understand dynamic

time-varying factors) and between subjects and these data will be linked to the available treatment outcome data including follow-ups.

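### A biosensor effect on an Aim 1 outcome, even one equal in both arms, would cut the later Aim 1 and 2 analyses from 200 to 140 participants

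*Combined protocol and SAP*

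**What the plan says.** Under the overall analysis strategy in Section I, item 13, the plan checks for assessment reactivity by asking whether biosensor use (yes/no) affects the Aim 1 primary outcomes, "as either a main effect, or interacting with medication". The consequence is: "If this is found, then all subsequent analyses for Aims 1 & 2 will be limited to the sample (n=140) without the biosensor assessment".

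Other statements bear on this:

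- Item 13: "Primary analyses will be based on an intent-to-treat basis", "Primary outcomes will be tested at the two-sided alpha 0.05 threshold" and "If normality is not satisfied, transformations or nonparametric alternatives will be considered".
- Item 1 states Primary Aim 2 as "among all participants (n=50 per cell, N=200 total").
- Item 4 (Overview of Study Design) plans the monitoring "during the first 6 weeks of the 12-week treatment period in a subset of participants (n=15 per cell, n=60 total"). The biosensor procedures repeat the window: "Participants will wear the system for the first six weeks of the 12-week medication period".
- Biosensor use is not described as randomised. The biosensor procedures make it depend on equipment being available when treatment starts. Section II, Devices, item 4(e) also requires a completed first lab session. The lab procedures make those sessions optional for trial participants.

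**The concern.** **The analysis set depends on outcome data.** A test on the primary outcomes decides whether 60 randomised participants count. NB versus placebo among the other 140 is still a randomised comparison, but item 13 does not reconcile the restriction with its intent-to-treat statement or with Aim 2 being stated for all 200.

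**A main effect is the wrong trigger.** A main effect means that monitored participants differ from unmonitored ones by the same amount in both arms. With users balanced across cells, that difference drops out of the NB-placebo contrast.

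**A trigger need not mean reactivity.** Because use is not randomised and may depend on completing an optional lab session, a main effect may reflect who was monitored.

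**The rule cannot be applied in only one way.** Item 13 gives no significance level for the trigger; 5% is a natural but unstated reading. It does not say whether one of the two Aim 1 outcomes is enough, whether the trigger tests are adjusted for multiplicity, or whether an N=200 Aim 1 result is replaced.

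**Aim 2 can lose more than 30%.** If the lab-session requirement for devices is applied, all 60 users have first-session lab data, while everyone who declined or could not be scheduled is among the 140.

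**Working it through.** **Inputs from the documents.** 4 cells of 50, 1:1 allocation, 15 biosensor users per cell, two-sided 5% for primary outcomes. The plan's figure reproduces: 200 − 60 = 4 × (50 − 15) = 140, or 70 per arm, with 30 users per arm.

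**Assumptions.** Unit SD, 5% per trigger test, one outcome, and N=140 replaces N=200 when triggered. The documents give no effect size or power, so I use the effect with 80% power at N=200: 2.80 × √(4/200) = 0.396 SD.

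**1. Precision.** Let D0 be the NB effect in the 140 and D1 that in the 60.

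- var D0 = 4/140 = 0.0286; var D1 = 4/60 = 0.0667.
- The full-sample estimate is F = 0.7·D0 + 0.3·D1, with var F = 0.02.
- SE ratio = √(200/140) = 1.195 (variance +43%).
- Power at 0.396 SD in the 140 is 65%.
- For weight in patients with obesity (50 against 35 per arm), the difference detectable with 80% power goes from 0.560 to 0.670 SD.

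**2. How often the rule fires with no biosensor effect.** 1 − 0.95² = 9.75%. If either of two outcomes suffices, four independent tests give 1 − 0.95⁴ = 18.5%.

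**3. Type I error.**

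- F is uncorrelated with the interaction estimate: 0.3 × 0.0667 − 0.7 × 0.0286 = 0.
- D0 is correlated with it: −√(0.0286/0.0952) = −0.548.
- So P(reject in the 140) is 21.4% given the interaction trigger, about 5% given the main-effect trigger, and 13.0% given either.
- Overall: 0.9025 × 5% + 0.0975 × 13.0% = 5.8%. Simulation agrees. The 0.8-point excess comes from the interaction trigger.

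**4. Power at 0.396 SD.**

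| True balanced shift | Rule fires | Power under rule | Power at N=200 |
|---|---|---|---|
| none | 9.75% | 78% | 80% |
| 0.3 SD (assumed) | about 52% | about 72% | 80% |

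The larger a harmless shift is, the more often precision is given up.

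**5. If the target is the NB effect without monitoring.**

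- With no biosensor effect, root mean squared error is 0.141 SD at N=200, 0.169 at N=140 and about 0.15 under the rule.
- With an interaction I, the N=200 mean squared error is 0.02 + 0.09·I². It equals 0.0286 at I = 0.31 SD, which means monitoring removes 78% of a 0.396 SD effect.
- N=140 has more power only if 0.396 − 0.3·I < 0.396·√0.7, so I > 0.216 SD (54% removed).
- The interaction SE is √(4/140 + 4/60) = 0.309. The test has 17% power at 0.31 SD and needs about 0.86 SD for 80%.

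**6. Non-additive case (assumed).** If monitoring cuts binge eating by 30% in both arms, the raw N=200 difference is 0.7 + 0.3 × 0.7 = 0.91 of the unmonitored one. On a log scale the shift cancels.

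**7. Aim 2, with L of 200 having lab data (L is not stated) and all 60 users among them.**

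| L | Left | Loss | SE ratio √(L/(L−60)) | Power at 0.396 SD |
|---|---|---|---|---|
| 200 | 140 | 30% | 1.20 | 80% → 65% |
| 160 | 100 | 37.5% | 1.26 | 71% → 51% |
| 120 | 60 | 50% | 1.41 | 58% → 33% |

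**The case against.** - **The average harm is small.** With no biosensor effect the rule costs 0.8 points of type I error and about 2 points of power, and a main-effect-only rule leaves type I error at 5%. The bigger loss needs a reactivity shift that nothing in the documents supports. This stands and limits the severity.
- **The rule is prespecified, treats the arms alike and has a stated purpose.** That limits discretion, but it supplies no reason to drop participants on a main effect.
- **Only subsequent analyses are limited, so the N=200 Aim 1 result may stand.** This is a fair reading, and under it the Aim 1 figures above do not apply to the first primary test. Aim 2 and follow-up analyses would still shrink, and the ambiguity itself needs resolving.
- **Restriction protects the question of medication alone.** The Background (Section I, item 3) describes a medication-only test, but in contrast to behavioural treatment; extending that to monitoring is an inference. Even granting it, the full sample is more accurate unless monitoring removes most of the NB effect.
- **Cancellation needs additivity and actual balance.** This is correct. Item 13 leaves the scale open, 15 per cell is only a plan, and equipment decides use. The 30% example shows a modest attenuation of 9%.
- **Selection through the lab-session requirement is uncertain.** Some participants may have their first session at weeks 4–6, which does not fit wearing the device from week 1 under that requirement. The selection and Aim 2 points are therefore conditional on its being applied.

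**Conclusion.** The concern holds, as something that should be fixed rather than a threat to the trial's validity. A biosensor main effect alone can reduce the later Aim 1 and 2 analyses to 140. For a shift that is additive and balanced, this removes no bias, multiplies the SE by 1.195 and lowers an assumed 80% power to 65% in the restricted set. The interaction trigger adds a slight excess of type I error (5.8% overall). These error rates assume 5% trigger tests, one outcome and replacement of the N=200 result; none of these is stated. Attrition that is equal in users and non-users leaves the SE ratio unchanged. At the 20% and 38% cited in the section on treatment completion rates, the detectable difference goes from 0.44 to 0.53 SD and from 0.50 to 0.60 SD.

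**What to change.** Delete the restriction in item 13 and replace it with text to this effect:

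- All randomised participants form the primary analysis set for Aims 1 and 2; for lab outcomes, all those with lab data.
- The biosensor-by-medication interaction, the NB effect by biosensor group and the n=140 analysis are reported as sensitivity analyses, whatever the result of any reactivity test.
- For follow-up analyses, a biosensor user is someone who wore it in the first 6 weeks of treatment. Later entry to the separate Biosensor Arm does not change this.

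Adding biosensor use as a covariate is a useful option if actual numbers depart from 15 per cell.

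The cost is about two sentences of analysis text and slightly more reporting, with no new data. The downside is that, if monitoring truly changes the NB effect, the primary estimate averages over monitored and unmonitored participants; the sensitivity analyses address this.
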